10.1.4 RETENTION IN TREATMENT

Duration of treatment is defined as the time from the first dose of CAM2038 to the last dose plus 28 days if the last treatment was CAM2038 q4w or plus 7 days if the last treatment was CAM2038 q1w.

Duration of treatment will be summarized by the percentage of patients retained in treatment by week. Data will also be presented using Kaplan-Meier plots.

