9. STUDY PROCEDURES AND ASSESSMENTS

All study assessments will be performed at the visits and time points outlined in the Schedule of Assessments ([Table 3](#)); the following sections outline the details and procedures associated with the assessments. Additional details on the assessments, including copies of questionnaires, logs, manuals, and information sheets are provided in the Study MOP.

Table 3: Schedule of Assessments

Study Phase:	Screening	Treatment Phase						EOT	Follow-up
Treatment:	-	CAM2038 q1w or q4w	CAM2038 q1w			CAM2038 q4w			All Subjects
Study Population:	All Subjects ^a	All Subjects	New to BPN Treatment ^b	Transition from SL BPN/BPX ^c	Transition from CAM2038 q1w ^d	Transition from SL BPN/BPX (Monthly) ^e			
Month ^f :	M-1	M1	M1	M1 to Mx	M1 to Mx	Mx to M12 ^g	M1 to M12 ^h		M13
Week ^h :	-3	W1	W1	W2 to Wx ⁱ	W1 to Wx ⁱ	Wx to W48	W1 to W48	W49	W53
Day:	-	Day 1	Day 2-7 ^j	-	-	-	-		-
Informed Consent ^k	X								
Eligibility Criteria Review ^l	X	X							
Medical and Medication Hx	X								
Substance Abuse/Treatment Hx (questionnaires)	X								
DSM-V	X								
Physical Examination ^m	X								

^a All subjects will undergo screening procedures.

^b Subjects seeking treatment with BPN, but treatment with BPN has not yet begun.

^c Subjects receiving SL BPN/BPX at the time of study entry and considered by the Investigator to be a candidate for CAM2038 q1w once weekly treatment.

^d Subjects who started treatment with CAM2038 q1w and are transitioned to CAM2038 q4w after meeting criteria.

^e Subjects receiving SL BPN/BPX at the time of study entry and considered by the Investigator to be a candidate for CAM2038 q4w once monthly treatment.

^f A window of ±7 days will be allowed for monthly visits.

^g The last monthly injection will be administered at the end of Month 11 (Week 45); additional assessments will be performed at the Week 49 visit, including transition back to usual care.

^h A window of ±3 days will be allowed for weekly visits.

ⁱ Subjects may transition to CAM2038 q4w and monthly visits at any time during the 12 months, once they meet criteria for transitioning (Section 7.1.2).

^j A window of ±1 day will be allowed for the visit performed on Day 4.

^k Subjects must voluntarily provide written informed consent prior to any study-related procedures being performed.

^l Prior to enrollment in the Treatment Phase of this study, all Inclusion and Exclusion criteria must be met.

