5.2 FULL EXPOSURE SAFETY POPULATION

All patients who have been exposed to CAM2038 for 48 weeks.

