10.0 EFFICACY ANALYSES

10.1.1 EFFICACY VARIABLES

This is a long-term safety study and efficacy evaluation is not the primary objective of the study. All efficacy variables will be summarized using the efficacy population. The efficacy variables will include the following:

- Urine toxicology results for illicit opioids
- Self-reported illicit opioid use
- Retention (%) in treatment (identical to exposure)
- Retention (%) in study
- Measures of opioid withdrawal:
 - Clinical Opiate Withdrawal Scale (COWS)
 - Subjective Opiate Withdrawal Scale (SOWS)

- Measures of opioid craving:
 - Desire to Use Visual Analogue Scale (VAS)
 - Need to Use VAS
- Urine toxicology results for other drugs of abuse
- Work Productivity and Activity Impairment Questionnaire General Health (WPAI-GH)
- EQ-5D-5L Health Questionnaire
- Patient Satisfaction Scale

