10.1.5 RETENTION IN STUDY

Duration in study is defined as the time from first dose of CAM2038 to the date of study discontinuation.

Duration in study will be summarized by the percentage of patients retained in the study by week. Data will also be presented using Kaplan-Meier plots.

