11.1.1 EXTENT OF EXPOSURE

Summary statistics (number and percentage) of weeks of exposure to study drug (i.e. from the date of the first injection to the date of the last injection plus 28 days if the last treatment was CAM2038 q4w or plus 7 days if the last treatment was CAM2038 q1w) will be presented. Number of patients, number of

injections and exposure years will be presented by dose, treatment (CAM2038 q1w and CAM2038 q4w) and in total.

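### Retention in treatment runs to the last injection plus 28 or 7 days with no cut-off at study discontinuation or death, so it can outlast retention in study, and exposure can accrue after death (minor)

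*SAP*

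**What the plan says.** SAP 10.1.4 defines the treatment measure: "Duration of treatment is defined as the time from the first dose of CAM2038 to the last dose plus 28 days" where the last treatment was q4w, or "plus 7 days if the last treatment was CAM2038 q1w". On its use the section says: "Duration of treatment will be summarized by the percentage of patients retained in treatment by week". Kaplan-Meier plots are also planned.

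SAP 11.1.1 counts exposure in the same way, "from the date of the first injection to the date of the last injection plus 28 days" or plus 7 for q1w, and feeds it into weeks of exposure and exposure years. SAP 10.1.1 ties the two together by listing "Retention (%) in treatment (identical to exposure" as an efficacy variable.

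SAP 10.1.5 ends the companion measure elsewhere: "Duration in study is defined as the time from first dose of CAM2038 to the date of study discontinuation". It too is shown by week and by Kaplan-Meier plot.

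SAP 5.2 defines the Full Exposure Safety Population as "All patients who have been exposed to CAM2038 for 48 weeks", without saying how exposure is computed for that purpose. Protocol Table 3, footnote g, fixes the end of monthly dosing: "The last monthly injection will be administered at the end of Month 11 (Week 45", with the end-of-treatment visit at Week 49.

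Protocol 7.6 lists withdrawal of consent, loss to follow-up and death among the ways a patient leaves. No section of either document truncates treatment duration or exposure at those events. SAP Appendix B deals only with partial dates for adverse events and medications.

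**The concern.** Protocol 7.6 allows a patient to stop study drug and stay under assessment, so time in treatment should not exceed time in study. Under the SAP rules it can. A patient who dies or withdraws 2 days after a q4w injection is out of the study on that day in the 10.1.5 tables, yet is retained in treatment for 26 more days in the 10.1.4 tables. The two Kaplan-Meier figures could then contradict each other for the same patients.

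Three outputs are affected. Treatment retention is overstated for these patients. The overstatement depends on the product, and because new entrants start on q1w, it may differ between the groups in the planned tables by new-to-treatment status. Exposure years can include days after death. If the 11.1.1 formula also decides who has 48 weeks of exposure, a patient can enter the Full Exposure Safety Population without having stayed in the study for 48 weeks.

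**Working it through.** **Inputs.** Added days of 28 (q4w) and 7 (q1w): SAP 10.1.4 and 11.1.1. Last q4w injection at Week 45: Protocol Table 3, footnote g. Last q1w injection taken as Week 48, from the weekly schedule in the same table. Dropout of 50% and 228 enrolled: SAP 7.0, used only for scaling. The dropout pattern and the q1w/q4w mix are not given and are assumed below.

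**The 48-week figure on the nominal schedule.**
- q4w: (45 − 1) × 7 + 28 = 308 + 28 = 336 days = 48.0 weeks.
- q1w: (48 − 1) × 7 + 7 = 329 + 7 = 336 days = 48.0 weeks.

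For patients who stay, the rule returns the intended 48 weeks.

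**One patient who leaves or dies g days after the last injection.** Excess of treatment duration over study duration = 28 − g (q4w) or 7 − g (q1w).
- q4w: g = 1 gives 27 days; g = 14 gives 14; g = 27 gives 1.
- q1w: g = 1 gives 6 days; g = 6 gives 1.
- A q4w patient leaving the day after the Week 45 injection has 308 + 1 = 309 days (44.1 weeks) in study but 336 days of computed exposure.
- A q1w patient leaving the day after the Week 48 injection has 329 + 1 = 330 days (47.1 weeks) against 336.

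**Effect on the retention percentages.** Assume a constant hazard, S(t) = (1 − D)^(t/48), with D the dropout by Week 48. Just before the next injection is due, everyone who left during the current interval still counts as retained. The SAP figure is then S(t − 4) on q4w or S(t − 1) on q1w, against a truncated S(t). This is the largest gap within an interval.

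| D | Week | Truncated | SAP, all q4w | Gap (patients of 228) | SAP, all q1w | Gap (patients of 228) |
|---|---|---|---|---|---|---|
| 50% | 4 | 94.4% | 100% | 5.6 (12.8) | 95.8% | 1.4 (3.1) |
| 50% | 24 | 70.7% | 74.9% | 4.2 (9.6) | 71.7% | 1.0 (2.3) |
| 50% | 48 | 50.0% | 53.0% | 3.0 (6.8) | 50.7% | 0.7 (1.7) |
| 30% | 48 | 70.0% | 72.1% | 2.1 (4.8) | 70.5% | 0.5 (1.2) |

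An assumed 50:50 product mix at D = 50% gives 1.9 points (4.2 patients) at Week 48.

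**Average over an interval (D = 50%).** The mean time since the last injection is 2 weeks on q4w and 0.5 week on q1w.
- q4w: S(46) − S(48) = 51.5% − 50.0% = 1.5 points; S(22) − S(24) = 72.8% − 70.7% = 2.1 points.
- q1w: S(47.5) − S(48) = 50.4% − 50.0% = 0.4 point; S(23.5) − S(24) = 71.2% − 70.7% = 0.5 point.

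Patients whose departure is recognised only because the next injection was missed contribute nothing to any of these gaps.

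**The case against.** The best defence is that the added days describe the product. Protocol 5.1.1 and 5.1.2 describe release over one and four weeks, and Protocol 8.7 says receptor occupancy may last up to two weeks (q1w) or a month (q4w) after the last injection. The SAP openly labels treatment retention as exposure and reports the discontinuation-based measure separately (Tables 14.2.5.1 and 14.2.5.2, Figure 14.2.2). This stands for exposure in a living patient. It does not justify exposure after death, or calling a patient who has left the study retained in treatment.

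A reader might infer that the last weeks of a patient's 48-week safety experience went unobserved. The documents do not support that in general. Protocol 9.4.1.1 follows adverse events for 30 days after early termination, SAP 11.1.2 tabulates events with onset before the last dose plus 30 days, and Protocol 7.6 asks sites to continue safety assessments. What remains is mainly withdrawn consent, loss to follow-up and death.

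A reader might also take 3 to 4 points as the expected bias. Those figures are ceilings: all patients on q4w, the curve read just before an injection is due, and every departure dated within the interval. Not everyone can be on q4w, because new entrants start on q1w.

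Nor is it established that the Full Exposure Safety Population is wrongly composed, since SAP 5.2 does not say that the 11.1.1 formula sets it.

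The error is not always upward. If an 8 mg q1w booster counts as the last treatment, a q4w patient whose last injection is a booster on day 3 computes to 3 + 7 = 10 days instead of 28.

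Finally, efficacy is exploratory and descriptive (Protocol 9.5 and 11.3.2), no planned retention table is split by product, and no sample size or test depends on retention.

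**Conclusion.** The point holds as a minor one. Followed exactly, the SAP counts some dead or departed patients as retained in treatment while its companion measure counts them as out of the study, by up to 27 days (q4w) or 6 days (q1w) per patient. It also lets exposure years accrue after death. The per-patient limits follow from the definitions alone, for departures from the day after an injection onwards. The population figures rest on an assumed constant hazard, the SAP's 50% dropout and an unknown product mix: at Week 48 at most 3.0 points (all q4w) or 0.7 point (all q1w), with interval averages of about 1.5 to 2 points and 0.5 point or less. Fewer departures dated between injections would make the effect smaller. The primary safety conclusions do not turn on it.

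**What to change.** - **SAP 10.1.4:** end retention in treatment at the earliest of last injection plus 28 or 7 days, date of study discontinuation, and death. The discontinuation date is already needed for 10.1.5, and the SAP plans a listing of death reports. The rule should not rely on a separate treatment-discontinuation date, because neither document shows that one is recorded.
- **SAP 10.1.1:** delete the parenthetical statement that treatment retention and exposure are the same.
- **SAP 11.1.1:** keep depot coverage as the exposure measure, truncated at death.
- **SAP 5.2:** state whether the 11.1.1 formula sets the Full Exposure Safety Population. If it does, report how many of its members were still in the study through Week 48. Truncation at death alone leaves a living patient who departs after the Week 45 injection at 336 days, so only this count shows the difference.

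The cost is a few sentences in the SAP and one extra table row. Reported retention in treatment would fall by up to a few points.

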10.1.5 RETENTION IN STUDY

Duration in study is defined as the time from first dose of CAM2038 to the date of study discontinuation.

Duration in study will be summarized by the percentage of patients retained in the study by week. Data will also be presented using Kaplan-Meier plots.

10.1.6 MEASURES OF OPIOID WITHDRAWAL

Measures of withdrawal include COWS and SOWS. The COWS is comprised of 11 items, each with a score of 0 through 4 or 5. Higher scores are associated with greater withdrawal symptoms. The items are meant to be objective measures of a patient's withdrawal symptoms (e.g., resting pulse rate). The SOWS is comprised of 16 items each with a score of 0 through 4. Higher scores are associated with greater withdrawal symptoms. The items are statements that are evaluated by the patient and are therefore subjective (e.g., I feel anxious, 0 = not at all, 1 = a little, 2 = moderately, 3 = quite a bit, 4 = extremely).

If there are ≥ 3 (i.e., $\geq 20\%$) missing items in the COWS scale at a given visit or ≥ 4 (i.e., $>20\%$) missing items in the SOWS scale at a given visit, the COWS/SOWS score for that visit will be missing. If there are 1 or 2 missing items for the COWS assessment then the total of the non-missing items will be calculated and the product of the calculated total and $11/(11 - \# \text{ missing})$ will be used for the COWS score

for that visit. If 3 or fewer items are missing for the SOWS score then the total of the non-missing items will be calculated and the product of the calculated total and $16/(16 - \# \text{ missing})$ will be used for the SOWS score.

COWS and SOWS data will be presented by visit. Data will also be presented as change from baseline by subtracting the baseline values from the post-baseline values. Negative changes are thus indicative of improvement.

10.1.7 MEASURES OF OPIOID CRAVING

Measures of craving include Desire to Use VAS and Need to Use VAS and will be assessed using unipolar 100 mm VAS; “Since your last scheduled assessment visit, indicate your worst or strongest desire/need to use opioids between 0 = No desire/need to use and 100 = Maximum desire/need to use on this scale”.

VAS data for Desire to Use and Need to Use will be presented by visit. Data will also be presented as change from baseline by subtracting the baseline values from the post-baseline values. Negative changes are thus indicative of improvement.

10.1.8 URINE TOXICOLOGY RESULTS FOR OTHER DRUGS OF ABUSE

Percentage of patients with urine samples positive for other drugs of abuse will be presented by week and month. Mean percentage of urine samples positive for other drugs of abuse will also be presented. Due to the flexible visit schedule, no imputation of missing data will be applied.

10.1.9 WORK PRODUCTIVITY AND ACTIVITY IMPAIRMENT QUESTIONNAIRE GENERAL HEALTH (WPAI-GH)

Data for WPAI-GH will be presented by item over time.

10.1.10 EQ-5D-5L HEALTH QUESTIONNAIRE

Data for EQ-5D-5L will be presented over time.

10.1.11 PATIENT SATISFACTION SCALE

Patient satisfaction scale scores will be presented by item over time.

11.0 SUMMARIES OF MEASURES OF SAFETY

Safety analyses will be performed for the overall safety population and full exposure safety population.

Safety evaluations will be based on the incidence, intensity and type of adverse events (AEs), as well as on clinically significant changes in the patient’s vital signs, electrocardiogram (ECG), clinical laboratory results and injection site examinations.

11.1.1 EXTENT OF EXPOSURE

Summary statistics (number and percentage) of weeks of exposure to study drug (i.e. from the date of the first injection to the date of the last injection plus 28 days if the last treatment was CAM2038 q4w or plus 7 days if the last treatment was CAM2038 q1w) will be presented. Number of patients, number of

injections and exposure years will be presented by dose, treatment (CAM2038 q1w and CAM2038 q4w) and in total.

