7.1.2.3. Treatment Visits (Weeks 2 to 48)

Subjects will return to clinic for visits based on each subject's dose of CAM2038 (q1w – once weekly or q4w – once monthly).

Subjects receiving **CAM2038 q1w** will return to the clinic weekly to receive their next dose and for safety and other assessments as outlined in [Table 3](#). At the discretion of the Investigator, subjects may receive dose adjustments during the scheduled CAM2038 q1w weekly dose visits (up to a maximum weekly dose of 40 mg per week).

Subjects may return to the clinic for additional titration with CAM2038 q1w (8 mg SC booster injections) as needed (i.e., at unscheduled visits), up to a maximum weekly dose of 40 mg per week.

At any weekly visit, the Investigator may transition subjects from weekly (CAM2038 q1w) to monthly (CAM2038 q4w) clinic visits after, at the minimum, taking the following criteria into consideration on the day of the visit where the transition of dose will occur (ie. Prior to new dose administration):

- Subject is on a stable dose of CAM2038 q1w without any additional fluctuations in dose for 4 weeks
- Subject has minimal subjective and no objective withdrawal symptoms, based on the SOWS and COWS scores (SOWS \leq 7 and COWS \leq 5).
- Subject exhibits diminished desire/need to use, based on VAS scores.

- Subject has diminished use of illicit opioids, according to the Investigator's discretion

Subjects who are eligible for **transitioning from CAM2038 q1w to CAM2038 q4w** will be transitioned in the following manner:

- Subjects will receive a single CAM2038 q4w SC injection, using the following conversion guidelines:
 - 16 mg (0.32 mL) CAM2038 q1w: 64 mg (0.18 mL) CAM2038 q4w
 - 24 mg (0.48 mL) CAM2038 q1w: 96 mg (0.27 mL) CAM2038 q4w
 - 32 mg (0.64 mL) CAM2038 q1w: 128 mg (0.36 mL) CAM2038 q4w

In addition, per Investigator's discretion, subjects may be switched back from monthly CAM2038 q4w visits to CAM2038 q1w weekly visits at any time during the Treatment Phase, if weekly dose visits are deemed to be appropriate based on the Investigator's clinical judgment on subject's level of stability.

Subjects receiving **CAM2038 q4w** will return to the clinic monthly to receive their next dose, and for safety and other assessments outlined in [Table 3](#).

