Subjects may receive temporary dose adjustment while receiving CAM2038 q4w, at the Investigator's discretion, using booster CAM2038 q1w 8 mg SC injections at any time during the study (through unscheduled visits, as needed). At the discretion of the Investigator, subjects may also receive dose adjustments during the scheduled CAM2038 q4w monthly dose visits. The temporary dose adjustments, or booster CAM2038 q1w 8 mg SC injection may be given at a maximum of two boosters per week.

At each visit (weekly or monthly), the following will be assessed:

- Urine samples for opioid toxicology, evaluated using immunoassay (qualitative) with reflex quantitative confirmation methods. Urine will also be tested for other drugs of abuse (e. g., cocaine, benzodiazepines, barbiturates, amphetamines, phencyclidine, and THC) and for alcohol using qualitative methods.
- Self-reported use of all drugs, including illicit or prescription opioids and other prescribed or illicit drugs.
- Measures of withdrawal using the Clinical Opioid Withdrawal Scale (COWS) and the Subjective Opioid Withdrawal Scale (SOWS)
- Measures of craving using Desire to Use and Need to Use visual analog scales (VAS)
- Other safety assessments and measures as outlined in [Table 3](#).

7.1.3. Follow-up Phase (Week 49 to 53):

Following the last Treatment Visit, subjects will be transitioned to standard care (e.g., SL BPN/BPX) at Week 49. Additional assessments will be performed during Week 53 outlined in [Table 3](#).

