9.3.7. Unscheduled Visits, Medication and Counseling

Temporary adjustments in BPN doses will be allowed using CAM2038 q1w SC booster injections (8 mg) at unscheduled visit(s). A maximum of two SC booster injections will be allowed per week. Subject-requested or physician-directed supplemental visits, phone calls or additional counseling, or other pharmacological interventions, along with the reason(s) for unscheduled visits, booster injections, phone calls or additional counseling or other pharmacological interventions, will be recorded.

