4.2 STUDY TREATMENTS

Following Screening, qualified patients will be initiated on either CAM2038 q1w or q4w, based on their current treatment status (qualified patients currently on sublingual (SL) BPN or seeking BPN treatment). Qualified patients will be initiated or transitioned to CAM2038 q1w or q4w as follows:

- Initiation of BPN treatment – initiate with CAM2038 q1w
- Currently receiving SL BPN treatments – transfer to corresponding CAM2038 q1w or q4w dose

Patients will be allowed to receive supplemental BPN during the study with booster SC injections of CAM2038 q1w 8 mg up to a maximum dose of 40 mg CAM2038q1w per week. For patients on CAM2038 q4w, a maximum of two booster doses of CAM2038 q1w 8 mg SC injections may be given per week. Dose adjustments (up or down titrations) will also be allowed at scheduled visits.

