| LISTING 16.2.9 | C-SSRS |
| LISTING 16.2.10 | Physical Examination |
| LISTING 16.2.11 | Vital Signs |
| LISTING 16.2.12 | 12-Lead ECG |
| LISTING 16.2.13 | Patient Visits |

List of Figures

| | |
|---------------|---|
| FIGURE 14.2.1 | Kaplan-Meier Plot of Time to Treatment Discontinuation (retention in treatment) (Efficacy Population) |
| FIGURE 14.2.2 | Kaplan-Meier Plot of Time to Study Discontinuation (retention in study) (Efficacy Population) |
| FIGURE 14.2.3 | Urine Toxicology Results for Illicit Opioid Use Supported by Self-Reported Illicit Opioid Use by Time (Efficacy Population) |
| FIGURE 14.2.4 | Urine Toxicology Results for Illicit Opioid Use Without Self-Reported Illicit Opioid Use by Time (Efficacy Population) |

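### When a patient's final injection is a q1w dose given less than 21 days after a q4w dose, the exposure and retention rule discards q4w credit that is still running

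*SAP*

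**What the plan says.** SAP 11.1.1 measures weeks of exposure from the date of the first injection to the date of the last, "plus 28 days if the last treatment was CAM2038 q4w or plus 7 days if the last treatment was CAM2038 q1w". SAP 10.1.4 gives retention the same form: "Duration of treatment is defined as the time from the first dose of CAM2038 to the last dose plus 28 days" for q4w, with 7 days for q1w. SAP 10.1.1 ties the two together by listing "Retention (%) in treatment (identical to exposure").

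Two features of the treatment plan mix the products within a patient.

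- **Boosters.** SAP 4.2 states: "For patients on CAM2038 q4w, a maximum of two booster doses of CAM2038 q1w 8 mg SC injections may be given per week". Protocol 7.1.2.3 allows temporary adjustment on q4w "using booster CAM2038 q1w 8 mg SC injections at any time during the study", and Protocol 9.3.7 repeats the ceiling: "A maximum of two SC booster injections will be allowed per week".
- **Switch-back.** Under Protocol 7.1.2.3, "subjects may be switched back from monthly CAM2038 q4w visits to CAM2038 q1w weekly visits at any time during the Treatment Phase".

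Neither SAP 10.1.4 nor 11.1.1 mentions boosters or says what to do when the credits of the two products overlap.

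**The concern.** The rule looks only at the last injection. If that is a q1w dose given while a q4w credit is still running, the rule replaces the rest of the 28 days with 7 days from the later date. The patient has received more drug and is credited with less exposure.

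Exposure is a core output of a 48-week safety study. Because retention is defined as identical to it, the same dates feed the weekly retention tables and the figure titled "Kaplan-Meier Plot of Time to Treatment Discontinuation (retention in treatment) (Efficacy Population"). The wording also leaves a choice to the programmer. The date comes from the last injection, but the size of the credit comes from the last treatment, which can be read as the product injected or as the regimen. For boosters the two readings give different answers, and neither is right in general.

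**Working it through.** **Inputs.** Credits of 28 days (q4w) and 7 days (q1w): SAP 11.1.1 and 10.1.4. Last monthly injection at Week 45: Protocol Table 3, footnote g. Weekly dosing to Week 48: Protocol Table 3. Visit windows of ±7 days (monthly) and ±3 days (weekly): Table 3, footnotes f and h. Full exposure of 48 weeks = 48 × 7 = 336 days: SAP 5.2. The first injection is day 0.

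**1. Reproduce the plan's figure.** On-schedule q4w completer: (45 − 1) × 7 + 28 = 308 + 28 = 336 days. On-schedule q1w completer: (48 − 1) × 7 + 7 = 329 + 7 = 336 days. Without mixing, the rule returns exactly 48 weeks.

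**2. General form.** Let the final injection be q1w, d days after the last q4w dose. Counting from that q4w dose:

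- by product name: d + 7
- by regimen, dated from a booster: d + 28
- booster ignored: 28
- later of the two credits: max(28, d + 7)

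By product name, the shortfall is 28 − (d + 7) = 21 − d for 0 < d < 21, and zero from d = 21. By regimen, the excess is d up to d = 21, and 21 after that. Ignoring the booster is correct up to d = 21 and then d − 21 days short.

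**3. Booster as final injection after an on-schedule Week 45 q4w dose (days from first injection).**

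| d | By product | By regimen | Booster ignored | Later of the two credits |
|---|---|---|---|---|
| 1 | 316 | 337 | 336 | 336 |
| 7 | 322 | 343 | 336 | 336 |
| 14 | 329 | 350 | 336 | 336 |
| 20 | 335 | 356 | 336 | 336 |
| 28 | 343 | 364 | 336 | 343 |

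**4. Early stopper.** Last q4w dose at Week 5 (day 28), final q1w dose 7 days later (day 35). By product: 35 + 7 = 42 days (6.0 weeks). The q4w credit runs to 28 + 28 = 56 days (8.0 weeks), so 14 days are lost. If the q1w dose was a switch-back rather than a booster, product and regimen are both q1w, and both readings give this loss.

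**5. Where there is no loss.** If weekly q1w continues until the final dose falls at d ≥ 21, then d + 7 ≥ 28. A switch-back at a scheduled monthly visit falls on day 28 ± 7, that is day 21 to 35, so d ≥ 21 already.

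**6. How many patients.** This cannot be derived, because the documents give no booster or switch-back frequency. For scale only, assume 10 patients each losing 20 days. That is 200 days, against 100 × 336 = 33,600 days from 100 full exposures alone: 200/33,600 = 0.6%.

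**7. A strict 336-day cut.** A Week 45 q4w dose given 7 days early yields 301 + 28 = 329 days. A Week 48 q1w dose given 3 days early yields 326 + 7 = 333 days. Both patients are in window, neither had a booster, and both miss 336.

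**The case against.** The strongest reply is that the last treatment means the regimen. SAP 11.1.1 goes on to use treatment as a label for q1w versus q4w, and boosters are described elsewhere as supplemental or temporary. On that reading a booster does not shorten exposure. This stands in part: for boosters, the undercount depends on the product-name reading. It does not rescue the rule, because the date is still that of the last injection, and a booster is an injection. Adding 28 days from there overcounts by up to 21 days. For switch-back the reply has no force.

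It is also fair that 28 and 7 days are bookkeeping conventions. Protocol 5.4 gives at least 28 days of stable levels for q4w, and Protocol 8.7 gives longer receptor dissociation for q1w. The errors above are therefore measured against the SAP's own credits, not against true drug effect.

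A reader might infer three stronger things that the documents do not support.

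- *Any q1w dose within 20 days of a q4w dose shortens exposure.* Only the patient's final injection matters, and a switch-back must be off schedule.
- *Completers will drop out of the Full Exposure Safety Population.* SAP 5.2 and Protocol 11.2 require 48 weeks but do not say that SAP 11.1.1 decides membership or how the cut is applied.
- *Week-48 retention falls by a known amount.* Assuming 228 patients in the Efficacy Population and retention meaning a duration of at least 7w days at week w, each affected completer would cost 1/228 = 0.44 percentage points. The SAP states neither. If retention means entering week 48 (more than 329 days), boosters at d = 15 to 20 cost nothing. SAP 10.1.4 also gives no event or censoring rule for the Kaplan-Meier plot.

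**Conclusion.** Wrong as written; minor to moderate severity. When the final injection is a q1w booster, or a q1w dose after an off-schedule switch-back, given 1 to 20 days after the last q4w dose, the rule applied by product name ends exposure and retention 20 to 1 days too early by the SAP's own credits. For boosters, the regimen reading errs the other way by d days, up to 21.

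The arithmetic is certain; the number of patients is unknown. Overall Safety Population membership is unaffected. Adverse event tabulation is also unaffected, since SAP 11.1.2 uses the last dose plus 30 days. Efficacy, including retention, is exploratory (Protocol 9.5). Injections are listed (Listing 16.2.5.1), so results could be re-derived. The effect on the Full Exposure Safety Population is possible but conditional: if SAP 11.1.1 with a 336-day cut decided membership, the completers in the table with d = 1 to 20 would be excluded on the product-name reading.

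**What to change.** In SAP 10.1.4 and 11.1.1, state: *End of exposure is the latest of (each q4w injection date + 28 days) and (each q1w or booster injection date + 7 days).* This leaves on-schedule completers at 336 days, treats boosters and switch-backs alike, and removes the choice between readings.

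In SAP 5.2, say whether exposure under 11.1.1 decides membership. If it does, the rule should allow for the ±7-day monthly and ±3-day weekly windows, because a strict 336-day cut would exclude the in-window completers at 329 and 333 days, whom the new sentence does not help.

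The cost is a few lines of SAP text and the matching derivation before database lock, with no new data. The sentence settles total exposure and retention only. SAP 11.1.1 still needs a line on how days covered by both products are divided when exposure years are split by dose and product. Like the present rule, it does not look at gaps between injections.
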